6.5.4.2 Severe Hypersensitivity Reactions and Flu-like Symptoms

If hypersensitivity reaction occurs, the subject must be treated according to the best available medical practice. A complete guideline for the emergency treatment of anaphylactic reactions according to the Working Group of the Resuscitation Council (United Kingdom) can be found at <https://www.resus.org.uk/pages/reaction.pdf>. Subjects should be instructed to report any delayed reactions to the Investigator immediately.

A. Symptoms

- Impaired airway
- decreased oxygen saturation (< 92%)
- confusion
- lethargy
- hypotension
- pale/clammy skin

- cyanosis

B. Management

[figure not shown]
1. Epinephrine injection and dexamethasone infusion
2. Patient should be placed on monitor immediately
3. Alert intensive care unit (ICU) for possible transfer if required

For prophylaxis of flu-like symptoms, 25 mg indomethacin or comparable NSAID dose (e.g., ibuprofen 600 mg, naproxen sodium 500 mg) may be administered 2 hours before and 8 hours after the start of each dose of avelumab i.v. infusion. Alternative treatments for fever (e.g., paracetamol) may be given to subjects at the discretion of the investigator.

6.5.4.3 Tumor Lysis Syndrome

In addition, since avelumab can induce ADCC, there is a potential risk of tumor lysis syndrome. Should this occur, subjects should be treated as per local guidelines and the management algorithm (Figure 6.1) published by Howard et al (56).

Figure 6.1 Assessment and Initial Management of Tumor Lysis Syndrome (TLS)

6.5.4.4 Immune-Related Adverse Events

Since inhibition of PD-L1 stimulates the immune system, irAEs may occur. Treatment of irAEs is mainly dependent upon severity (NCI-CTCAE grade):

- Grade 1 to 2: treat symptomatically or with moderate dose steroids, more frequent monitoring
- Grade 1 to 2 (persistent): manage similar to high grade AE (Grade 3 to 4)
- Grade 3 to 4: treat with high dose corticosteroids

Treatment of irAEs should follow guidelines set forth in [Table 6.2](#).

Table 6.2 Management of Immune-Related Adverse Events

Gastrointestinal irAEs		
Severity of Diarrhea / Colitis (NCI-CTCAE v4)	Management	Follow-up
Grade 1 Diarrhea: < 4 stools/day over Baseline Colitis: asymptomatic	Continue avelumab therapy Symptomatic treatment (e.g., loperamide)	Close monitoring for worsening symptoms Educate subject to report worsening immediately If worsens: Treat as Grade 2 or 3/4
Grade 2 Diarrhea: 4 to 6 stools per day over Baseline; i.v. fluids indicated < 24 hours; not interfering with ADL Colitis: abdominal pain; blood in stool	Delay avelumab therapy Symptomatic treatment	If improves to Grade 1: Resume avelumab therapy If persists > 5 to 7 days or recur: 0.5 to 1.0 mg/kg/day methylprednisolone or equivalent When symptoms improve to Grade 1, taper steroids over at least 1 month, consider prophylactic antibiotics for opportunistic infections, and resume avelumab therapy per protocol. If worsens or persists > 3 to 5 days with oral steroids: Treat as Grade 3 to 4
Grade 3 to 4 Diarrhea (Grade 3): ≥ 7 stools per day over Baseline; incontinence; i.v. fluids ≥ 24 hrs; interfering with ADL Colitis (Grade 3): severe abdominal pain, medical intervention indicated, peritoneal signs Grade 4: life-threatening, perforation	Discontinue avelumab therapy per protocol 1.0 to 2.0 mg/kg/day methylprednisolone i.v. or equivalent Add prophylactic antibiotics for opportunistic infections Consider lower endoscopy	If improves: Continue steroids until Grade 1, then taper over at least 1 month If persists > 3 to 5 days, or recurs after improvement: Add infliximab 5 mg/kg (if no contraindication), Note: Infliximab should not be used in cases of perforation or sepsis

Dermatological irAEs		
Grade of Rash (NCI-CTCAE v4)	Management	Follow-up
Grade 1 to 2 Covering ≤ 30% body surface area	Symptomatic therapy (for example, antihistamines, topical steroids) Continue avelumab therapy	If persists > 1 to 2 weeks or recurs: Consider skin biopsy Delay avelumab therapy Consider 0.5 to 1.0 mg/kg/day methylprednisolone i.v. or oral equivalent. Once improving, taper steroids over at least 1 month, consider prophylactic antibiotics for opportunistic infections, and resume avelumab therapy If worsens: Treat as Grade 3 to 4
Grade 3 to 4 Covering > 30% body surface area; life threatening consequences	Delay or discontinue avelumab therapy Consider skin biopsy Dermatology consult 1.0 to 2.0 mg/kg/day methylprednisolone i.v. or i.v. equivalent	If improves to Grade 1: Taper steroids over at least 1 month and add prophylactic antibiotics for opportunistic infections Resume avelumab therapy
Pulmonary irAEs		
Grade of Pneumonitis (NCI-CTCAE v4)	Management	Follow-up
Grade 1 Radiographic changes only	Consider delay of avelumab therapy Monitor for symptoms every 2 to 3 days Consider Pulmonary and Infectious Disease consults	Re-image at least every 3 weeks If worsens: Treat as Grade 2 or Grade 3 to 4
Grade 2 Mild to moderate new symptoms	Delay avelumab therapy Pulmonary and Infectious Disease consults Monitor symptoms daily, consider hospitalization 1.0 mg/kg/day methylprednisolone i.v. or oral equivalent Consider bronchoscopy, lung biopsy	Re-image every 1 to 3 days If improves: When symptoms return to near baseline, taper steroids over at least 1 month and then resume avelumab therapy and consider prophylactic antibiotics If not improving after 2 weeks or worsening: Treat as Grade 3 to 4

Grade of Pneumonitis (NCI-CTCAE v4)	Management	Follow-up

Grade 3 to 4 Severe new symptoms; New / worsening hypoxia; life-threatening
	
Discontinue avelumab therapy Hospitalize Pulmonary and Infectious Disease consults 2 to 4 mg/kg/day methylprednisolone i.v. or i.v. equivalent Add prophylactic antibiotics for opportunistic infections Consider bronchoscopy, lung biopsy
	
If improves to baseline: Taper steroids over at least 6 weeks If not improving after 48 hours or worsening: Add additional immunosuppression (for example, infliximab, cyclophosphamide, i.v. immunoglobulin, or mycophenolate mofetil)

Hepatic irAEs		
Grade of Liver Test Elevation (NCI-CTCAE v4)	Management	Follow-up

Grade 1 Grade 1 AST or ALT > ULN to 3.0 x ULN and / or total bilirubin > ULN to 1.5 x ULN
	
Continue avelumab therapy
	
Continue liver function monitoring If worsens: Treat as Grade 2 or 3 to 4

Grade 2 AST or ALT > 3.0 to ≤ 5 x ULN and / or total bilirubin > 1.5 to ≤ 3 x ULN
	
Delay avelumab therapy Increase frequency of monitoring to every 3 days
	
If returns to baseline: Resume routine monitoring, resume avelumab therapy If elevations persist > 5 to 7 days or worsen: 0.5 to 1 mg/kg/day methylprednisolone or oral equivalent and when LFT returns to Grade 1 or Baseline, taper steroids over at least 1 month, consider prophylactic antibiotics for opportunistic infections, and resume avelumab therapy

Grade 3 to 4 AST or ALT > 5 x ULN and / or total bilirubin > 3 x ULN
	
Discontinue avelumab therapy Increase frequency of monitoring to every 1 to 2 days 1.0 to 2.0 mg/kg/day methylprednisolone i.v. or i.v. equivalent Add prophylactic antibiotics for opportunistic infections Consult gastroenterologist Consider obtaining MRI/CT scan of liver and liver biopsy if clinically warranted
	
If returns to Grade 2: Taper steroids over at least 1 month If does not improve in > 3 to 5 days, worsens or rebounds: Add mycophenolate mofetil 1 gram (g) twice daily If no response within an additional 3 to 5 days, consider other immunosuppressants per local guidelines

Cardiac irAEs		
Myocarditis	Management	Follow-up
New onset of cardiac signs or symptoms and / or new laboratory cardiac biomarker elevations (e.g. troponin, CK-MB, BNP) or cardiac imaging abnormalities suggestive of myocarditis	
Withhold avelumab therapy.
 
Hospitalize.
 
In the presence of life threatening cardiac decompensation, consider transfer to a facility experienced in advanced heart failure and arrhythmia management.
 
Cardiology consult to establish etiology and rule out immune-mediated myocarditis.
 
Guideline based supportive treatment as per cardiology consult.^a
 
Consider myocardial biopsy if recommended per cardiology consult.
	
If symptoms improve and immune-mediated etiology is ruled out, re-start avelumab therapy.
 
If symptoms do not improve/worsen, viral myocarditis is excluded, and immune-mediated etiology is suspected or confirmed following cardiology consult, manage as immune-mediated myocarditis.

Immune-mediated myocarditis	
Permanently discontinue avelumab.
 
Guideline based supportive treatment as appropriate as per cardiology consult.^a
 
Methylprednisolone 1 to 2 mg/kg/day.
	
Once improving, taper steroids over at least 1 month and add prophylactic antibiotics for opportunistic infections.
 
If no improvement or worsening, consider additional immunosuppressants (e.g. azathioprine, cyclosporine A)

a Local guidelines, or eg. European Society of Cardiology or American Heart Association guidelines
 
European Society of Cardiology guidelines website: https://www.escardio.org/Guidelines/Clinical-Practice-Guidelines
 
American Heart Association guidelines website: http://professional.heart.org/professional/GuidelinesStatements/searchresults.jsp?q=&y=&t=1001
		
Endocrine irAEs		
Endocrine Disorder	Management	Follow-up
Asymptomatic TSH abnormality	
Continue avelumab therapy
 
If TSH < 0.5 x LLN, or TSH > 2 x ULN, or consistently out of range in 2 subsequent measurements: include T4 at subsequent cycles as clinically indicated; consider endocrinology consult
	
Symptomatic endocrinopathy	
Evaluate endocrine function
 
Consider pituitary scan
 
Symptomatic with abnormal lab / pituitary scan:
	
If improves (with or without hormone replacement):
 
Taper steroids over at least 1 month and consider prophylactic antibiotics for opportunistic infections

	
Delay avelumab therapy
 
1 to 2 mg/kg/day methylprednisolone iv or by mouth equivalent
 
Initiate appropriate hormone therapy
 
Endocrinology consult to distinguish (differentiate) between primary from secondary dysfunction. No abnormal lab/pituitary MRI scan but symptoms persist:
 
Repeat labs in 1 to 3 weeks/MRI in 1 month
	
Resume avelumab therapy
 
Subjects with adrenal insufficiency may need to continue steroids with mineralocorticoid component

Suspicion of adrenal crisis (for example, severe dehydration, hypotension, shock out of proportion to current illness)
	
Delay or discontinue avelumab therapy
 
Rule out sepsis
 
Stress dose of i.v. steroids with mineralocorticoid activity
 
i.v. fluids
 
Consult endocrinologist
 
If adrenal crisis ruled out, then treat as above for symptomatic endocrinopathy
	

ADL=activities of daily living, ALT=alanine aminotransferase, AST=aspartate aminotransferase, CT=computerized tomography; irAE=immune-related adverse event, iv=intravenous, LFT=liver function test, LLN=lower limit of normal, MRI=magnetic resonance imaging, NCI-CTCAE=National Cancer Institute-Common Terminology Criteria for Adverse Event, NSAID=non-steroidal anti-inflammatory drugs, T4=free thyroxine, TSH=thyroid-stimulating hormone, ULN=upper limit of normal.

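### Protocol Section 6.5.4.4 sends persistent Grade 1–2 irAEs to Grade 3–4 management without defining persistence, and Table 6.2 does not carry this through: the hepatic row clearly conflicts, and the rash row conflicts on the steroid step

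*Protocol*

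**What the plan says.** Section 6.5.4.4 of the protocol opens with three bullets that set irAE treatment by grade. The first allows Grade 1–2 events symptomatic care or a moderate steroid dose, with closer monitoring. The second reads "Grade 1 to 2 (persistent): manage similar to high grade AE (Grade 3 to 4". The third reads "Grade 3 to 4: treat with high dose corticosteroids". None of them gives a dose, a time threshold or an effect on avelumab, and *persistent* is not defined.

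The next sentence says "Treatment of irAEs should follow guidelines set forth in" Table 6.2. That table has its own persistence steps:

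- Hepatic, Grade 2, elevations lasting beyond 5–7 days: "0.5 to 1 mg/kg/day methylprednisolone or oral equivalent and when LFT returns to Grade 1 or Baseline, taper steroids", after which avelumab resumes.
- Rash, Grade 1–2, lasting beyond 1–2 weeks: delay avelumab and "Consider 0.5 to 1.0 mg/kg/day methylprednisolone i.v. or oral equivalent", then resume once improving.
- Diarrhoea/colitis, Grade 2: "If persists > 5 to 7 days or recur: 0.5 to 1.0 mg/kg/day methylprednisolone or equivalent", resuming at Grade 1.

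For Grade 3–4 diarrhoea/colitis the table says "Discontinue avelumab therapy per protocol", and the hepatic Grade 3–4 row also discontinues. Both give 1.0–2.0 mg/kg/day.

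Section 5.1.7.2 lets treatment resume after a Grade 2 adverse drug reaction has settled to Grade 1 or below, and refers irAEs to Section 6.5.4.4 as a whole.

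**The concern.** A site treating a persistent Grade 2 liver-test rise finds two instructions in one section. The bullet points to Grade 3–4 management, which in the hepatic row means stopping avelumab and the higher steroid band. The Grade 2 hepatic row points to the lower band and resumption. Section 5.1.7.2 refers to the whole section, so it brings in both.

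The first stake is patient safety: which steroid step is used and, for hepatic events, whether avelumab continues.

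The second is the safety analysis. Expansion SAP Section 17.1.5 tabulates irAEs leading to permanent discontinuation. Table 15 in Appendix II of that SAP makes corticosteroid or other immunosuppressant treatment one of the criteria for classifying an event as immune-related (hormone replacement can also serve for endocrinopathies). For persistent rash, one reading only asks the site to consider systemic steroids and the other specifies them. The reading followed could therefore affect whether the event meets the case definition.

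**Working it through.** No sample size, power or event count is involved, so the check sets the passages side by side. All entries are from Table 6.2; doses are methylprednisolone in mg/kg/day.

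| Row | Persistence trigger | Steroid step | Avelumab | Step to Grade 3–4 management | Grade 3–4 row |
|---|---|---|---|---|---|
| Hepatic, Grade 2 | more than 5–7 days, or worsening | 0.5–1 | delayed, then resumes | none | discontinue; 1.0–2.0 |
| Rash, Grade 1–2 | more than 1–2 weeks, or recurrence | 0.5–1.0, to be considered | delayed, then resumes | on worsening only | delay or discontinue; 1.0–2.0; resumption allowed after improvement to Grade 1 |
| Diarrhoea/colitis, Grade 2 | more than 5–7 days, or recurrence | 0.5–1.0 | delayed, resumes at Grade 1 | on worsening, or after more than 3–5 days on oral steroids | discontinue; 1.0–2.0 |
| Pneumonitis, Grade 2 | no improvement after 2 weeks, or worsening | 1.0 from the start | delayed, resumes after taper | yes, at that trigger | discontinue; 2–4 |

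The cardiac and endocrine rows are not split into these grades, so the comparison does not apply to them.

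*Two readings of the bullet.* Because persistence is undefined, it can mean (A) the table's first persistence trigger, or (B) an event still present after the moderate steroid dose named in the first bullet.

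- **Hepatic.** Under A, the bullet and the row give different steroid bands and opposite outcomes for avelumab. Under B, the bullet requires a step that the row does not contain. They do not agree on either reading.
- **Rash.** Under A, the steroid step differs: 0.5–1.0 to be considered, against 1.0–2.0. Under B, the row again lacks the step, since it escalates only on worsening. Resumption does not separate the grades, because the Grade 3–4 row also permits it.
- **Diarrhoea/colitis.** Under A there is a conflict in dose and in the effect on avelumab. Under B there is none: the row moves to Grade 3–4 management after the further 3–5 days.
- **Pneumonitis.** The row agrees with the bullet.

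*Dose.* For the first three rows, lower limits: 1.0 / 0.5 = 2. Upper limits: 2.0 / 1.0 = 2. Each limit of the Grade 3–4 band is twice its lower-grade counterpart. The bands share one value, 1.0 mg/kg/day, so a subject on that dose satisfies both.

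*Section 5.1.7.2.* Its Grade 2 rule, to withhold and then resume at Grade 1 or below, matches the table's Grade 2 rows on avelumab. It does not match the bullet if Grade 3–4 management is taken to include stopping avelumab.

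**The case against.** The strongest reply is that the bullets are a sketch and the table is the working instruction. The bullets give no dose or timing, say only that management is similar, and are followed by a sentence directing treatment to Table 6.2. Taken in order they describe a ladder: symptomatic care, then moderate steroids, then Grade 3–4 management. The diarrhoea and pneumonitis rows fit that ladder. The bullets also concern treatment of the irAE; stopping avelumab enters only through the table's Grade 3–4 rows, and Section 5.1.7.2 supports resumption after Grade 2.

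Much of this stands, and it removes several stronger readings that a reader might draw:

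- *The bullet contradicts every organ row.* It does not: pneumonitis agrees, and diarrhoea agrees on the stepwise reading.
- *For rash, the choice is between resuming and stopping avelumab.* The Grade 3–4 rash row also allows resumption.
- *The steroid dose is always doubled.* The limits are doubled, but the bands meet at 1.0 mg/kg/day.
- *Most irAEs are affected.* Section 3.4 counts 26 Grade 1 and 29 Grade 2 events among 69 potential irAEs (55 of 69). That count covers all organ systems, whether or not the event persisted, and is not a count of affected subjects.
- *Sites have already diverged.* The documents report no such differences.

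The reply does not dispose of the hepatic row or the rash steroid step. The ladder is one possible reading, not a stated rule, and the hepatic Grade 2 row has no upper rung. Directing sites to the table is not the same as saying that the table overrides a bullet in the same section.

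**Conclusion.** The inconsistency is real but narrower than a comparison of the bullet with the whole table would suggest. It is clear for persistent Grade 2 liver-test elevations, where both the steroid band (0.5–1 against 1.0–2.0 mg/kg/day) and the effect on avelumab (resume against discontinue) differ. It is confined to the steroid step for persistent Grade 1–2 rash. It is conditional on the meaning of persistence for Grade 2 diarrhoea/colitis, and absent for Grade 2 pneumonitis.

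The number of subjects concerned cannot be derived from the documents. Any effect on discontinuation rates, steroid use or irAE classification is a possibility that follows from the wording, not an observed result.

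The conclusion rests on reading the bullet as an instruction, since the section does not mark it as a summary or subordinate it to the table. It takes no view on which management step is clinically right.

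**What to change.** Reconcile the bullet on persistent Grade 1–2 events with the persistence steps in Table 6.2 and with the Grade 2 rule in Section 5.1.7.2. There are two ways to do it: make all three state the same step and the same effect on avelumab, with *persistent* defined; or say expressly in Section 6.5.4.4 which of the bullet and the table governs. The hepatic Grade 2 and rash Grade 1–2 rows need attention first. The sponsor's clinical team decides the content.

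The cost is about a line of protocol wording. It needs no additional subjects, procedures or analyses.

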6.6 Packaging and Labeling

Avelumab is formulated as a 10.0 mg/mL or 20 mg/mL solution in single-use glass vials, with a rubber stopper. The Clinical Trial Supplies department of the Sponsor will supply the trial medication of avelumab, which will be distributed to the sites by the CRO.

Packaging and labeling will be in accordance with applicable local regulatory requirements and applicable Good Manufacturing Practice (GMP) guidelines. Avelumab will be packed in boxes containing a suitable number of vials. The information on the medication will be in accordance with approved submission documents.

Avelumab will be shipped in transport cool containers (2°C to 8°C) that are monitored with temperature control devices.

6.7 Preparation, Handling and Storage

For application in this trial, avelumab drug product must be diluted with 0.9% saline solution (sodium chloride injection) supplied in an infusion bag. Detailed information on infusion bags and medical devices to be used for the preparation of the dilutions and subsequent administration will be provided in the MOP.

Avelumab drug product must be stored at 2°C to 8°C until use, with a temperature log maintained daily. All medication boxes supplied to each study center must be stored carefully, safely, and separately from other drugs.

Avelumab drug product stored at room temperature (23°C to 27°C) or at elevated temperatures (38°C to 42°C) for extended periods is subject to degradation. Avelumab must not be frozen. Rough shaking of avelumab must be avoided.

Avelumab must not be used for any purpose other than the study. The administration of IMPs to subjects who have not been enrolled into the study is not covered by the study insurance.

The contents of the avelumab vials are sterile and nonpyrogenic, and do not contain bacteriostatic preservatives. Any spills that occur should be cleaned up using the facility's standard cleanup procedures for biologic products.

Any unused portion of the solution should be discarded in biohazard waste disposal with final disposal by accepted local and national standards of incineration.

6.8 Investigational Medicinal Product Accountability

The investigator is responsible for ensuring accountability for IMP, including reconciliation of drugs and maintenance of drug records.

- Upon receipt of IMP, the investigator (or designee) will check for accurate delivery and acknowledge receipt by signing (or initialing) and dating the documentation provided by the Sponsor and returning it to the Sponsor. A copy will be retained for the Investigator File.
- The dispensing of the IMP will be carefully recorded on the appropriate drug accountability forms provided by the Sponsor and an accurate accounting will be available for verification by the Sponsor monitor at each monitoring visit.
- IMP accountability records will include:
 - Confirmation of IMP delivery to the trial site.
 - The inventory at the site of IMP provided by the Sponsor and prepared at the site.
 - The use of each dose by each subject.
 - Destruction of unused treatment product (unused product will not be returned to the Sponsor).
 - Dates, quantities, batch numbers, expiry dates and (for IMP prepared at the site) formulation, as well as the subjects' trial numbers.
- The investigator should maintain records that adequately document:
 - That the subjects were provided the doses specified by the clinical trial protocol/amendment(s).
 - That all IMP provided by the Sponsor was fully reconciled.

Unused IMP must not be discarded or used for any purpose other than the present trial. IMP that has been dispensed to a subject must not be re-dispensed to a different subject.

The Sponsor monitor will periodically collect the IMP accountability forms and will check all returns (both unused and used containers) before authorizing their destruction by the trial site.

At the conclusion or termination of this study, site study personnel and the clinical study monitor will conduct a final product supply inventory on the Investigational Drug Accountability Forms and all unused containers will be destroyed. Instructions for destruction of product will be provided to the site. The clinical study monitor will be supplied with a copy for filing of the Investigational Drug Accountability Forms. This documentation must contain a record of clinical supplies used, unused and destroyed and shall include information on:

- All administered units.
- All unused units
- All destroyed units (during the study).
- All destroyed units at the end of the study.
- Date of destruction(s).
- Name and signature of the investigator/pharmacist.

In addition, it must be ensured at each study site that the study drug is not used:

- After the expiry date.
- After the retest date unless the study drug is reanalyzed and its retest date extended.

This is to be closely monitored by the study monitor.

